#### 10.2. Analysis Populations

The analysis populations are defined as follows:

- The enrolled safety population is defined as all enrolled subjects who receive at least 1 dose of open-label study drug treatment.
- The randomized safety population is defined as all randomized subjects who receive at least 1 dose of double-blind study drug treatment.
- The ITT population is defined as randomized subjects who receive at least 1 dose of double-blind study drug treatment and have at least 1 post-dose assessment of the primary efficacy variable at both Visits 3 and 4.
- The clinically evaluable population is defined as all ITT subjects who have no major protocol deviations. This includes any subject who:
  - Received the morning dose of double-blind study medication at Visits 3 and 4
  - Completed all laboratory classroom assessments
  - Did not use prohibited medication during the double-blind Treatment Period.

The primary efficacy analyses will be performed on the ITT population. Secondary efficacy analyses on the ITT and clinically evaluable populations will be supportive of the primary analysis.

The safety analyses will be performed on the enrolled and randomized safety populations.

Deviations from the original statistical plan as planned in this protocol will be reported and justified in the SAP and clinical study report (CSR) as appropriate.

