#### 4.3. Subject Withdrawal Criteria

Within the provisions of informed consent/assent and good clinical judgment with respect to the subject's safety, every attempt should be made to have subjects complete the study. The following are possible reasons to terminate the participation of any subject from the study:

- Signs and symptoms of intolerance to the study medication.
- A treatment-related, serious adverse event (SAE) is observed.
- The subject or parent/guardian is grossly non-compliant, as determined by the Investigator.
- Continued participation, in the opinion of the Investigator, is no longer in the best interest of the subject.
- The subject or parent/guardian wishes to withdraw for any reason.

• Unblinding of the Investigator, site personnel performing assessments, or subject/parent to a subject's treatment assignment during the double-blind Randomization Treatment Period of the study.

Subjects will be encouraged to adhere to the protocol and complete all required assessments for the study. A subject may also be discontinued from the study for any of the following medical and/or administrative reasons:

- Pregnancy
- At the discretion of the Investigator at any time
- At the subject's request
- Occurrence of a treatment-emergent AE or considerable worsening of an AE that represents an unacceptable risk to the subject and when continued participation in the investigational study is not warranted, in the judgment of the Investigator or the Sponsor. The Investigator must follow the subject until the AE resolves or satisfactorily stabilizes.

Any enrolled subjects desiring to discontinue prior to study completion should be encouraged to continue in the study and adhere to the protocol and subsequent regularly scheduled safety and effectiveness evaluations. Subjects who are discontinued outside of any scheduled visit will be encouraged to complete the final study visit at the time of withdrawal. Subjects who are discontinued during a scheduled visit will be encouraged to complete all assessments for both that study visit and the final study visit at the time of withdraws following study drug administration will not be replaced.

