#### 5.3.1.5. Early Termination Visit

The following activities may be done for subjects that withdraw prior to completion of Study Visit 4 (i.e., terminate early):

- Blood pressure and pulse
- AE assessment
- Concomitant medications assessment
- Follow-up C-SSRS
- Study drug accountability and reconciliation
- A urine pregnancy test (for females of child-bearing potential only) may be performed in the event of a suspected pregnancy per Investigator's clinical judgment

For all activities performed, the results are to be recorded in the CRF.

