# 6. INVESTIGATIONAL DRUG INFORMATION AND MANAGEMENT

#### 6.1. Investigational Drug Dose Regimen

Open-label Dyanavel XR will be dispensed to enrolled subjects. Subjects will be instructed to take openlabel Dyanavel XR. Subjects who are stimulant naive will take Dyanavel XR beginning at 2 mL daily in the morning. Subjects who have a history of stimulant treatment may be initiated on open label Dyanavel XR at whole mL doses between 2 and 6 mL per day, inclusive, as selected by the investigator based on required doses for adequate symptom control with previous stimulant medication treatment. The dose for all subjects may be increased as tolerated as often as daily up to a maximum dose of 8 mL (20 mg) daily or until an optimal dose is reached as determined by the study doctor. The Investigator may decrease a subject's dose at any time during the open-label period to ensure tolerability. Subjects who find the maximum study dose of 8 mL (20 mg)/day is insufficient to treat their symptoms of ADHD and thus are not adequately controlled will be discontinued from the study.

The parents or guardians of the subjects will be instructed to administer the medication orally to their child once daily prior to 10 am with or without food. Children should not self-administer study medication.

During visits 3 and 4, and following randomization, subjects will receive Dyanavel XR 6 ml (15 mg), 7 mL (17.5 mg) or 8 mL (20 mg) or Placebo 6 mL, 7 mL or 8 mL once. The crossover treatment will be administered at the following double blind classroom session (Visit 4).

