# 8. RANDOMIZATION AND BLINDING PROCEDURES

Except for Visits 3 and 4, dosing will be conducted in an open-label fashion. The laboratory school days (Visits 3 and 4) and associated classroom testing will be performed in a double-blind manner. All double-blind study medication will be supplied in identical bottles and will be similar in physical characteristics (color, smell, and appearance), thereby enabling double-blind conditions.

Enrollment will occur after all screening procedures have been performed and eligibility for the study is confirmed at the Baseline (Visit 1).

At Visit 2 subjects will be randomized in a 1:1 ratio to treatment sequence: Dyanavel XR followed by Placebo or Placebo followed by Dyanavel XR.

Unblinding should occur only when knowing the treatment assignment has a bearing on the medical treatment or evaluation of a subject. Whenever possible, the need to unblind should be discussed with the Sponsor prior to unblinding-

A subsequent written report, including all pertinent details, must be submitted to the Sponsor within 24 hours of the unblinding. Whenever possible, the blind of the parent/guardian and subject should be maintained.

If an Investigator, site personnel performing assessments, or subject/parent is unblinded, the subject must be withdrawn from the study, and procedures accompanying withdrawal are to be performed.

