#### 10.3.2. Efficacy Analyses

#### 10.3.2.1. Primary Efficacy Analysis

The primary efficacy analysis will be performed on the ITT population. The primary efficacy outcome is change from pre-dose in the model-adjusted average of SKAMP-Combined score at 30 minutes post-dose.

The treatment difference will be estimated using least squares means from a mixed-effects repeated-measures model. The treatment comparison will be conducted as a 2-sided test at the 5% level of significance. All available data will be used; there will be no imputation of missing data. Effect size will be calculated.

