#### 10.5.2. Missing Data

Although the rate of missing data is expected to be low, missing data could occur under either or both of the following scenarios: missing or invalid data for individual questions in the SKAMP and missing SKAMP-Combined scores at individual time points.

In general, missing or invalid data for individual questions will be handled by rules specific to the validated SKAMP questionnaire and will be described in the SAP. No additional imputation for missing or invalid SKAMP responses will be performed.

No imputation of missing SKAMP-Combined scores will be done for the primary efficacy analysis. The mixed-model repeated-measures method used to analyze the primary endpoint has been designed to

utilize all available data and provides valid estimates under the assumption of data which are missing completely at random or missing at random. To evaluate the sensitivity of the primary analysis results to the use or non-use of imputation, analyses using single imputation (last observation carried forward) and multiple imputation methods may be conducted. This decision will be made prior to database unblinding, and the methods will be described in the SAP.

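### The ITT set requires a score at both double-blind visits, so a child who misses one whole visit drops out of every efficacy analysis, against the protocol's own missing-data rationale

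*Protocol*

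**What the plan says.** Section 10.2 of the protocol builds the primary analysis set from randomized children who took double-blind drug and who "have at least 1 post-dose assessment of the primary efficacy variable at both Visits 3 and 4". The primary analysis is run on this set. The clinically evaluable population is a subset of it, and the two safety populations serve safety only.

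Section 10.3.2.1 names a mixed-effects repeated-measures model on the ITT population and adds: "All available data will be used; there will be no imputation of missing data". Section 10.5.2 defends the absence of imputation by saying that the model was designed to "utilize all available data and provides valid estimates under the assumption of data which are missing completely at random or missing at random". It also says that "analyses using single imputation (last observation carried forward) and multiple imputation methods may be conducted" as a sensitivity check, with the decision left to the SAP.

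Children can leave between the two double-blind visits. Section 4.3 allows withdrawal at the family's wish, for intolerance or at the investigator's discretion. Section 8 says that after unblinding "the subject must be withdrawn from the study". The Early Termination list in section 5.3.1.5, "for subjects that withdraw prior to completion of Study Visit 4", contains no SKAMP. Section 4.3 also says, in a sentence that is garbled in the text at hand, that some withdrawals "following study drug administration will not be replaced".

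**The concern.** A mixed model is useful for missing data in a crossover because it can keep a child with one period. That child's observed score informs the period and treatment means, and its correlation with the missing score corrects for selective loss. Section 10.2 removes such a child before the model is fitted. The analysis then rests on children who attended both visits, a condition met or failed after randomization.

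This needs a stronger assumption than section 10.5.2 states: that loss after Visit 3 is unrelated to the Visit 3 score. Imputation run on the ITT set could not test that assumption, because a wholly missed visit never enters the set. At stake are the treatment estimate and the effect size that section 10.3.2.1 says will be reported, in a trial of about 15 randomized children.

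**Working it through.** **1. The texts side by side.** Take a child dosed and scored at Visit 3 who does not attend Visit 4.
- Section 10.2: not in ITT, so not in the clinically evaluable set.
- Section 10.3.2.1: the child's Visit 3 data exist, yet are not used.
- Section 10.5.2: validity under missing at random depends on the Visit 3 score being in the likelihood, and it is not.

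Now take a child who attends both visits but lacks one 30-minute score. SKAMP is rated at 30 minutes and 3 hours (section 5.2.1). If the primary variable in section 10.2 means SKAMP-Combined at any post-dose time, this child stays in ITT and the model can handle the gap. If it means the 30-minute score only, this child is excluded too.

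**2. The plan's own figure.** Section 10.1 gives effect size 1.00, about 15 randomized, 90% power, two-sided 0.05, 15% drop-out and about 18 enrolled.
- Take the effect on the SD of a single change score, with within-child correlation ρ. The standardized paired effect is 1/√(2(1−ρ)). At ρ = 0.4 this is 1/√1.2 = 0.913, and noncentral-t power with 15 children and 13 df is 90.4%.
- If the effect is already on the SD of the within-child difference, power is 94.7%.
- 15/0.85 = 17.6, so 18.

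The sizing reproduces and is not in question. The protocol does not give ρ, so 0.3, 0.4, 0.5 and 0.7 are used below as assumptions.

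**3. Why the bias can go either way.** Let change scores have SD 1, with higher meaning worse. The both-visits estimate averages, over the two sequences, the mean within-child placebo-minus-drug difference. Suppose loss lowers the mean Visit 3 residual of the remaining children by m_A in the active-first sequence and m_P in the placebo-first sequence. Their Visit 4 residuals fall by ρ·m_A and ρ·m_P. Hence

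bias = ((1−ρ)/2) × (m_A − m_P).

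If the worst Visit 3 scorers overall leave, most were on placebo that day. Then m_P exceeds m_A and the effect is understated. If the loss is among active-first children, the effect is overstated.

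Example: 8 active-first children, the 2 worst leave, none lost from the other sequence. The two largest of eight standard normal values have expectations of about 1.42 and 0.85, so m_A = (1.42 + 0.85)/6 = 0.38. The bias is 0.35 × 0.38 = 0.133 at ρ = 0.3, 0.30 × 0.38 = 0.114 at 0.4, 0.25 × 0.38 = 0.095 at 0.5 and 0.15 × 0.38 = 0.057 at 0.7. With 7 active-first children it is slightly larger.

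**4. Simulation.** Two-period crossover, 15 children, 2 lost after Visit 3, true effect 1.00. The model has treatment, visit and sequence.

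| Loss pattern | Quantity | ρ = 0.3 | 0.4 | 0.5 | 0.7 |
|---|---|---|---|---|---|
| Worst Visit 3 scores overall | Both-visits estimate | 0.91 | 0.92 | 0.93 | 0.96 |
| | Estimate, children kept | 1.00 | 1.00 | 1.00 | 1.00 |
| | Power, both-visits | 75.2% | 81.3% | 88.6% | 98.4% |
| | Power, children kept | 81.4% | 86.1% | 91.8% | 98.9% |
| Loss correlated 0.5 with Visit 3 score | Both-visits estimate | 0.98 | 0.98 | 0.98 | 0.99 |
| Random | Power, both-visits | 78.6% | 84.4% | 90.0% | 98.7% |
| | Power, children kept | 80.5% | 86.0% | 91.1% | 98.8% |

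- With only 1 child lost, worst score overall, the both-visits estimate is 0.95/0.95/0.97/0.98.
- When the 2 worst active-first scorers leave, it is about 1.05 to 1.13 across this range of ρ, in line with step 3. Keeping the children gives about 1.00.
- With no true effect and ρ = 0.4, both-visits rejection is 4.7 to 5.2% when loss treats the sequences alike. It is about 6% when loss falls on active-first children only (one run gave 7.0%).

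**The case against.** **The all-available-data sentence may mean all data within ITT.** Section 10.3.2.1 names the ITT population first, so this reading is possible and softens the conflict there. It does not rescue section 10.5.2, whose missing-at-random argument cannot reach a visit whose absence has already removed the child.

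**Requiring both periods is a familiar crossover choice.** A one-period child gives no within-child contrast. That supports a both-visits set as a supportive analysis. It does not fit the ITT label or the stated rationale for a mixed model.

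**Few children are likely to be lost.** Visit 4 is the weekend after Visit 3, section 4.3 asks that withdrawing children be encouraged to continue or to complete the final visit, and section 10.5.2 expects little missing data. This stands, and it limits the size of the point.

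Four stronger readings are tempting, and the documents do not support them:
- *That the model cannot use all available data or rely on missing at random at all.* Only whole missed visits are certainly affected. Time-point gaps may remain in the set.
- *That the bias is always toward no effect and Type I error is safe.* This holds only when loss treats both sequences alike. Step 3 shows the opposite sign when it does not.
- *That the full 15% drop-out, 3 of 18, could fall after randomization.* Section 10.1 counts about 15 as randomized out of about 18 enrolled, and enrolment precedes randomization (section 8).
- *That the 8 mL rule is a route out between Visits 3 and 4.* Section 6.1 says that a child for whom the maximum dose "is insufficient to treat their symptoms of ADHD and thus are not adequately controlled will be discontinued from the study", but does not say whether this applies after Visit 2. The point does not depend on it.

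**Conclusion.** The point holds for whole missed visits. The ITT definition discards children whose data the protocol says the model will use, and the missing-at-random justification does not cover that loss. The both-visits estimate is unbiased only if loss after Visit 3 is unrelated to the Visit 3 score, and otherwise neither the direction nor the Type I error can be taken for granted.

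The likely size is small. The extremes in the working need the worst scorers to leave deterministically. With 2 of 15 lost and a looser link to the Visit 3 score, the estimate is 0.98 to 0.99. With random loss there is no bias and the power difference is 0.1 to 1.9 points. The number lost, the correlation and the loss mechanism are all assumptions. This is a minor finding: an internal inconsistency worth correcting because the correction is nearly free.

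**What to change.** In section 10.2, define the ITT population as every randomized child who takes a double-blind dose and has a post-dose SKAMP-Combined score at Visit 3 or Visit 4. Fit the mixed model already named in section 10.3.2.1 to that set, and keep the both-visits set as a supportive analysis. Sections 10.2, 10.3.2.1 and 10.5.2 then agree, and any imputation analysis run on ITT would include missed visits.

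The cost is one reworded definition. It needs no extra children, visits, assessments or modelling.

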#### 10.3. Efficacy and Safety Analyses

#### **10.3.1.** Background and Demographic Characteristics

Baseline demographic variables will be reported.

#### 10.3.2. Efficacy Analyses

#### 10.3.2.1. Primary Efficacy Analysis

The primary efficacy analysis will be performed on the ITT population. The primary efficacy outcome is change from pre-dose in the model-adjusted average of SKAMP-Combined score at 30 minutes post-dose.

The treatment difference will be estimated using least squares means from a mixed-effects repeated-measures model. The treatment comparison will be conducted as a 2-sided test at the 5% level of significance. All available data will be used; there will be no imputation of missing data. Effect size will be calculated.

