#### 5.2. Efficacy and Safety Assessments

#### 5.2.1. Swanson, Kotkin, Agler, M-Flynn, and Pelham Rating Scale (SKAMP)

The SKAMP scale will be administered pre-dose, at 30 minutes and 3 hours post-dose during classroom sessions (visits 2, 3 and 4). Training on the SKAMP scale will be required for those who have not received training in the 12 months prior to performing this study assessment. Designated, qualified individuals from the study research team will perform the assessment.

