# **10. STATISTICS**

#### **10.1.** Power and Sample Size Determination

The primary efficacy outcome is change from pre-dose in the model-adjusted SKAMP-Combined score at 30 minutes hours post-dose as measured during the laboratory school days (Visits 3 and 4). Assuming an effect size of 1.00 between Dyanavel XR and placebo and approximately 15 subjects randomized to double-blind treatment, this study will have 90% power at the level of alpha = 0.05 (2-sided) to detect a treatment effect. To allow for an estimated 15% potential drop-out rate, this study plans to enroll approximately 18 subjects.

The assumed effect size is based on differences measured between active and placebo in previous laboratory school studies conducted with similar drug formulations at the earliest measured timepoint and reducing that by 20%.

A detailed statistical analysis plan (SAP) will be written and finalized prior to unblinding of the data.

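### Does analysing change from pre-dose, with no pre-dose covariate named, waste precision in a 15-child crossover?

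*Protocol*

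**What the plan says.** Section 10.3.2.1 of the protocol defines the endpoint: "The primary efficacy outcome is change from pre-dose in the model-adjusted average of SKAMP-Combined score at 30 minutes post-dose". The Synopsis and Sections 3.2.1 and 10.1 define it in the same way, each time with the qualifier model-adjusted, which is not explained. On the method, Section 10.3.2.1 says: "The treatment difference will be estimated using least squares means from a mixed-effects repeated-measures model". It names no fixed effects, random effects, covariance structure or covariates.

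Section 5.2.1 gives the measurement times: "The SKAMP scale will be administered pre-dose, at 30 minutes and 3 hours post-dose during classroom sessions (visits 2, 3 and 4"). A pre-dose score is therefore planned at each double-blind visit, as Section 5.3.1.4 and Appendix A confirm.

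Section 10.1 plans the size of the trial: "Assuming an effect size of 1.00 between Dyanavel XR and placebo and approximately 15 subjects randomized to double-blind treatment", and "this study will have 90% power at the level of alpha = 0.05 (2-sided) to detect a treatment effect". The same section promises a detailed SAP, finalized before unblinding.

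**The concern.** A change score without a pre-dose covariate gives the pre-dose score a fixed slope of 1. In a crossover, comparing each child with himself or herself already removes the stable child level. What is left in the pre-dose score is the state of that day plus rating noise. If that remainder predicts the 30-minute score only weakly, subtracting it carries noise into the treatment contrast, whereas an estimated slope would not.

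The claim of onset at 30 minutes rests on one contrast in about 15 children. The covariate would need no new data, and naming it would take one sentence. Precision would be at stake. Bias and type I error would not, because the change score is a valid outcome under randomisation.

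**Working it through.** **1. The plan's own figure.** Inputs from Section 10.1: effect size 1.00, about 15 children, two-sided alpha 0.05, power 90%. The section does not say which SD standardises the effect. Taking it as the SD of the within-child treatment difference:

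- Noncentrality = 1.00 × √15 = 3.87.
- Power at n = 15 is 94.9% on 14 df (paired t) or 94.7% on 13 df (crossover with a sequence term).
- The smallest n for 90% power is 13 (91.1% on 12 df, 90.6% on 11 df).
- Dropout: 15 / (1 − 0.15) = 17.6, rounded up to 18, as the protocol states.

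On this reading the unadjusted change score already exceeds the stated power. If 1.00 refers instead to the SD at a single visit, 90.4% is reached at n = 15 with an assumed between-visit correlation of 0.4.

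**2. What a covariate would do.** For each child take the active-minus-placebo difference in the pre-dose score and in the 30-minute score. Let r be their correlation and k the ratio of the post-dose to the pre-dose SD of these differences. The protocol gives neither, so both are assumptions.

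- Variance of the change-score contrast is proportional to 1 + k² − 2rk.
- Variance after adjustment is proportional to k²(1 − r²).
- Estimating the slope in 15 children, with a mean and a sequence term also fitted, multiplies the adjusted variance by 1 + 1/(15 − 4) = 1 + 1/11 = 1.09.
- The ratio, adjusted to unadjusted, is 1.09 × k²(1 − r²) / (1 + k² − 2rk). At k = 1 this becomes 1.09 × (1 + r)/2.

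| r | k = 0.7 | k = 1 | k = 1.3 |
|---|---|---|---|
| 0.3 | 0.45 | 0.71 | 0.88 |
| 0.5 | 0.51 | 0.82 | 0.995 |
| 0.7 | 0.53 | 0.93 | 1.08 |
| 0.8 | 0.52 | 0.98 | 1.09 |
| 0.9 | 0.44 | 1.04 | 1.00 |

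At r = 0 and k = 1 the ratio is 0.55. Simulation with an 8/7 sequence split agrees with the formula.

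At r = 0.5 and k = 1: 1.09 × 0.75 = 0.82. If the unadjusted power were exactly 90%, adjustment would give 94.5%. At r = 0.9 and k = 1 it would give 88.5%.

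At r = 0.7 and k = 1.3: 1.69 × 0.51 / (2.69 − 1.82) = 0.862 / 0.87 = 0.991, and 0.991 × 1.09 = 1.08.

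**3. Why the sign can turn.** The best slope is rk. When rk = 1 (r = 0.77 at k = 1.3) the change score is already optimal, and estimating the slope costs the full 9% in variance. A k above 1 is plausible, because the post-dose difference can carry child-to-child variation in drug response that the pre-dose difference lacks. Break-even on variance lies near r = 0.83 at k = 1 but near r = 0.5 at k = 1.3. At k = 1.3 and r = 0.8 the simulated mean confidence interval is about 5% wider with the covariate. At k = 1 and r = 0.9 it is about 2% wider.

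**4. What the text excludes.** Nothing in Section 10.3.2.1 rules out a pre-dose term. A change score can be analysed with the pre-dose score as covariate, and least squares means from a model described as adjusting the scores fit that reading. The section also leaves out treatment, period, sequence and subject, which any crossover analysis of this kind would have to specify. Silence on the pre-dose term is part of that general deferral.

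The calculation assumes that both 30-minute scores are present for each child. Section 10.2 requires only that a child "have at least 1 post-dose assessment of the primary efficacy variable at both Visits 3 and 4", which read literally a 3-hour score could satisfy.

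**The case for a change.** The best case for the concern is that the change score is fixed in the protocol in four places, and that Section 10.2 makes the protocol the reference against which later departures must be justified. Naming the covariate there would settle in advance whether adjustment was pre-specified. With equal variances the trade is lopsided: up to about 45% less variance at r = 0, against about 4% more at r = 0.9 and 6% at r = 0.95. At r = 0.5 the gain is like having about 18 children instead of 15 (15 / 0.82 = 18.3).

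The arithmetic stands under equal variances, and a sponsor could reasonably choose adjustment. It does not show a defect. A covariate added in the SAP would complete the protocol's model and would not depart from it. The lopsided trade rests on the equal-variance assumption, for which the protocol offers no figure. Nor does subtraction simply add noise unless r is close to 1. Against the raw 30-minute score with equal variances, it lowers the variance whenever 2(1 − r) < 1, that is, for r above 0.5.

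**Conclusion.** The concern does not hold. The protocol fixes a legitimate outcome and a model class, and leaves the model terms to the SAP, which is where covariates are commonly specified. As written, the plan yields an unbiased contrast with correct type I error and, on the within-child reading of the effect size, about 95% power at 15 children against the 90% claimed.

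The precision effect of a pre-dose covariate is real but of uncertain sign. Over r from 0.3 to 0.9 and SD ratios from 0.7 to 1.3, the variance ratio runs from about 0.44 to 1.09. Those ranges are assumptions, because the protocol reports neither quantity. Whether to spend a degree of freedom or two on baseline terms in so small a crossover is a choice on which statisticians may differ, and the text leaves it open.
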